23.1 Retention of clinical trial documentation

Patient's medical records must be kept for the maximum period permitted by the hospital, institution or private practice.

The investigator must agree to archive the documentation (this includes both electronic and paper-based records) pertaining to the trial in an archive after completion or discontinuation of the trial if not otherwise notified. The investigator should not destroy any documents without prior permission from Novo Nordisk. If the investigator cannot archive the documents at the trial site, Novo Nordisk can refer the investigator to an independent archive provider that has a system in place to allow only the investigator to access the files.

The investigator must be able to access his/her trial documents without involving Novo Nordisk in any way. Trial site-specific CRFs and other patient data (in an electronic readable format or as paper copies or prints) will be provided to the investigator before access is revoked to the systems and/or electronic devices supplied by Novo Nordisk. These data must be retained by the trial site. If the Novo Nordisk provided data (e.g. the CD-ROM) is not readable during the entire storage period, the investigator can request a new copy, as a copy of all data will be stored by Novo Nordisk.

Novo Nordisk will maintain Novo Nordisk documentation pertaining to the trial for as long as the product is on the market plus 20 years.

The files from the investigator trial site/institution must be retained for 15 years after the completion of the trial, or longer if required by national regulations. The deletion process must ensure confidentiality of data and must be done in accordance with local regulatory requirements.

23.2 Retention of human biospecimens

Storage and disposition of samples analysed at local laboratories will be performed according to local laboratory procedures.

Blood samples apart from antibody and biospecimen samples will be destroyed after the finalisation of the CTR. Antibody samples (samples for binding antibodies and inhibitors) will be stored until drug approval by Food and Drug Administration (FDA) and/or European Medicines Agency (EMA) or until the project terminates, but no longer than 15 years from end of trial. Biospecimens will be destroyed at the latest 15 years from end of trial. As new biomarkers related to the disease and/or safety, efficacy, or mechanism of action of N9-GP may evolve during the conduct of the trial, the analyses of the stored biospecimens may also include biomarkers that are unknown at present or have not been included in the scientific hypotheses at initiation of the trial. The samples will be stored at Novo Nordisk A/S or a Novo Nordisk designated referral bio-repository with access to the samples. Samples might be transferred to other countries, if not prohibited by local regulations. The

Protocol
Trial ID: NN7999-3895
UTN: U1111-1135-9557
EudraCT No.: 2012-004867-38

~~CONFIDENTIAL~~

| | | |
|----------|------------------|---------------------|
| Date: | 05 November 2019 | Novo Nordisk |
| Version: | 8.0 | |
| Status: | Final | |
| Page: | 114 of 119 | |

patient's identity will remain confidential and samples will only be marked and identified by a unique sample ID (patient number and visit number). No direct identification of the patient will be stored together with the samples. The analyses will not have any medical consequences for the patients or their relatives. Only Novo Nordisk staff and bio-repository personnel (if applicable) will have access to the stored bio specimens.

Protocol
 Trial ID: NN7999-3895
 UTN: U1111-1135-9557
 EudraCT No.: 2012-004867-38

~~CONFIDENTIAL~~

| | | |
|----------|------------------|---------------------|
| Date: | 05 November 2019 | Novo Nordisk |
| Version: | 8.0 | |
| Status: | Final | |
| Page: | 115 of 119 | |

24 Institutional Review Boards/Independent Ethics Committees and regulatory authorities

IRB/IEC:

Written approval or favourable opinion must be obtained from IRB/IEC prior to commencement of the trial.

During the trial, the investigator or sponsor, as applicable, must promptly report the following to the IRB/IEC, in accordance with local requirements: updates to IB, unexpected SAEs where a causal relationship cannot be ruled out, protocol amendments according to local requirements, deviations to the protocol implemented to eliminate immediate hazards to the patients, new information that may affect adversely the safety of the patients or the conduct of the trial (including new risk/benefit analysis in case it will have an impact on the planned follow-up of the patients), annually written summaries of the trial status, and other documents as required by the local IRB/IEC.

The investigator must ensure submission of the clinical trial report synopsis to the IRB/IEC (not applicable for Japan).

Protocol amendments must not be implemented before approval or favourable opinion according to local regulations, unless necessary to eliminate immediate hazards to the patients.

The investigator must maintain an accurate and complete record of all submissions made to the IRB/IEC. The records should be filed in the investigator's trial file and copies must be sent to Novo Nordisk.

Regulatory Authorities:

Regulatory authorities will receive the clinical trial application (CTA), protocol amendments, reports on SAEs, and the CTR according to national requirements.

Protocol
 Trial ID: NN7999-3895
 UTN: U1111-1135-9557
 EudraCT No.: 2012-004867-38

~~CONFIDENTIAL~~

| | | |
|----------|------------------|---------------------|
| Date: | 05 November 2019 | Novo Nordisk |
| Version: | 8.0 | |
| Status: | Final | |
| Page: | 116 of 119 | |

25 Indemnity statement

Novo Nordisk carries product liability for its products, and liability as assumed under the special laws, acts and/or guidelines for conducting clinical trials in any country, unless others have shown negligence.

Novo Nordisk assumes no liability in the event of negligence, or any other liability of the sites or investigators conducting the trial, or by persons for whom the said site or investigator are responsible.

Novo Nordisk accepts liability in accordance with:

Only applicable for Argentina: Novo Nordisk Pharma Argentina S.A. has contracted insurance (policy reference number 87828 and its respective updates) with the company [REDACTED]. Domiciled in [REDACTED]. Telephone number: [REDACTED].

Only applicable for Australia: Medicines Australia Guidelines for Compensation for Injury Resulting From Participation in a Company-sponsored Clinical Trial. Version 160104B dated 16 January 2004.

Only applicable for Austria: Arzneimittelgesetz (BGBl. Nr. 185/1983) last amended with BGBl. I Nr. 48/2013.

Only applicable for France: The French Public Health Code article L 1121-10 (law n° 2004-806 of 9 August 2004 art. 88 I, IX Journal Officiel of 11 August 2004. "The sponsor is responsible for identification of the harmful consequences of the biomedical research for the person lending himself thereto and for indemnification of his beneficiaries, except in case of proof, incumbent on it, that the prejudice is not attributable to his fault of or the fault of any intervening party, without the sponsor's being entitled to call on acts by a third party or the voluntary withdrawal of the person who had initially consented to cooperating in the research".

Only applicable for Netherlands: Wetgeving betreffende geneesmiddelen; geneesmiddelenwet 1 juli 2007 (Medicines Law, 1 July 2007). De Wet Medisch-wetenschappelijk Onderzoek met mensen (WMO), 1 maart 2006 (Medical Research Involving Human Subjects Act, 1 March 2006). Besluit verplichte verzekering bij medisch-wetenschappelijk onderzoek met mensen 2015, 24 november 2014 (Decree compulsory insurance in medical research involving human subjects 2015, 24 November 2014).

Only applicable for Poland: Novo Nordisk carries liability for the Study exclusively in the scope defined by the applicable laws and in particular by the Civil Code and the Pharmaceutical Law dated 6 September 2001 (uniform version Journal of Laws of 2008 No. 45 item 271 with amendments). In order to support potential claims for liability attributable to the Study, Novo

Protocol
Trial ID: NN7999-3895
UTN: U1111-1135-9557
EudraCT No.: 2012-004867-38

~~CONFIDENTIAL~~

| | | |
|----------|------------------|---------------------|
| Date: | 05 November 2019 | Novo Nordisk |
| Version: | 8.0 | |
| Status: | Final | |
| Page: | 117 of 119 | |

Nordisk and Investigator are covered by the Insurance Policy issued according to applicable Polish law’.

Protocol
 Trial ID: NN7999-3895
 UTN: U1111-1135-9557
 EudraCT No.: 2012-004867-38

~~CONFIDENTIAL~~

| | | |
|----------|------------------|---------------------|
| Date: | 05 November 2019 | Novo Nordisk |
| Version: | 8.0 | |
| Status: | Final | |
| Page: | 118 of 119 | |

26 References

## 1. Note

█ has prepared a Statistical Analysis Plan (SAP) for the Sponsor to review and sign-off for study NN7999-3895. Analyses will be conducted after this document has been finalized and officially signed. Anything in italics is taken directly from the protocol. For more details, please refer to the study protocol.

## 2. Version History

Version Number	Date	Reason for Revision
1.0	22 April 2019	Initial Version
2.0	15 July 2019	Revised based on sponsor requests

## 5. Abbreviations

### Abbreviation Description

ABAS-3	Adaptive Behavior Assessment System – Third Edition
BASC-3	Behavior Assessment System for Children – Third Edition
BRIEF2	Behavior Rating Inventory of Executive Function – Second Edition
BRIEF-A	Behavior Rating Inventory of Executive Function – Adult Edition
BRIEF-P	Behavior Rating Inventory of Executive Function – Preschool Edition
CI	Confidence Interval
DET	Detection Test
ED	Exposure Day (Definition: One exposure day is defined as each day when a patient is administered coagulation factor IX/blood components for any reason regardless number of doses)
FAS	Full Analysis Set
HNAS	Hemophilia Normative Analysis Set
IDN	Identification Test
IQR	Interquartile range (25th, 75th percentiles)
N9-GP	nonacog beta pegol, glycopegylated recombinant coagulation factor IX
ONB	One Back Test
SAP	Statistical Analysis Plan
SAS	Statistical Analysis Software
SD	Standard Deviation
SDH	Structured Development History
TLF	Tables, Listings, and Figures
WASI-II	Wechsler Abbreviated Scale of Intelligence – Second Edition
WPPSI-IV	Wechsler Preschool and Primary Scale of Intelligence – Fourth Edition
WSD	Within-Subject Deviation

## 6. Introduction

This Statistical Analysis Plan (SAP) contains a more technical and detailed elaboration of the principal features of the analysis described in the NN7999-3895 Study Protocol related to neurocognitive assessments and includes detailed procedures for executing the statistical analysis of the neurocognitive assessment data.

The SAP is finalized and signed prior to database lock. For operational efficiency, an earlier time is usually targeted. If needed, revisions to the approved SAP may be made prior to database lock. Revisions will be version controlled.

Any changes from the analyses planned in the SAP will be justified in the statistical report.

Prior to database lock, a dry run analysis will occur.

## 7. Study Objectives Related to Neurocognitive Assessments

To evaluate neurodevelopmental, neurocognitive and neurobehavioral outcomes on N9-GP exposed patients.

## 8. Study Design

### 8.1. General Description

Please see Sections 5, 8.1, and 8.2 of the study protocol for a general description of the study design.

### 8.2. Scheduled Visits

**Table 1: Visit Schedule for Neurocognitive Assessments**

Visit Number	Scheduled Interval	Analysis Visit
1, 20, 23, 26, 28-50	
 
BRIEF: Every 6 months (all countries)
 
██████ Battery: Every 6 months (all countries)
 
SDH: Every 6 months (all countries)
 
HH: Every 6 months (all countries)
 
Bayley-III / WPPSI-IV / WASI-II: Every 1 year (English-speaking countries only)
 
ABAS-3: Every 1 year (English-speaking countries only)
 
BASC: Every 1 year (English-speaking countries only)
 
	Yes
End of Trial		Yes
Unscheduled Visit		No

Study visits will be renamed such that the first visit is “Initial Assessment”, the next is “Assessment 2”, the following is “Assessment 3”, and so on, to account for the fact that not all subjects will be starting their neurocognitive assessments

at the same visit. If patients start on pre-prophylaxis and switch to prophylaxis at Visit 20, the assessments will be displayed under “Prophylaxis” in the tables.

The patient’s age when the Structured Developmental History (SDH) is completed will be used as the Visit Age for each visit.

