| 21 | Height will be collected at visit 0, visit 21, visit 23, visit 26, and at all visits from visit 28 to EOT visit. In case visit 1 is more than a month after visit 0, height needs to be redone at visit 1. For patients who have already attended visit 23 and 28 height at these two visits \pm 1 month will be collected retrospective if available in medical records upon parent(s)/LAR(s) consent . |
| 22 | Blood samples for PEG analysis should be taken at visit 0 taking the limitation of the allowed blood sampling volume into account. If not taken at visit 0, the blood sample should be taken at visit 1 pre-dose, if the blood volume allows. |
| 23 | Urine sample should be obtained if possible. It can be collected at home same day and brought to site if transported cold according to Section 8.4.2.8 . |
| 24 | The neurological examination can for all visits be made within \pm 1 month of the visits, except for the visit 1 and EOT visit where it can be made at visit date or up to 1 month ahead of the visit. |
| 25 | The neurocognitive assessments can for all visits be made within \pm 1 month of the visits, except for visit 1 and EOT visit where it can be made at visit date or up to 1 month ahead of the visit. For details see Table 8-1 and Table 8-2 . |

Protocol
 Trial ID: NN7999-3895
 UTN: U1111-1135-9557
 EudraCT No.: 2012-004867-38

~~CONFIDENTIAL~~

| | | |
|----------|------------------|---------------------|
| Date: | 05 November 2019 | Novo Nordisk |
| Version: | 8.0 | |
| Status: | Final | |
| Page: | 19 of 119 | |

3 Background information and rationale for the trial

The trial will be conducted in compliance with this protocol, ICH GCP¹ and applicable regulatory requirements, and in accordance with the Declaration of Helsinki.²

In this document, the term investigator refers to the individual responsible for the overall conduct of the clinical trial at a trial site.

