Conceptual Reasoning Domain Social Interactions Domain Practical Functioning Domain Adaptive Behavior Domain Score	Communication Skill Area Functional Pre-Academics Skill Area Self-Direction Skill Area Leisure Skill Area Social Skill Area Community Use Skill Area Home Living Skill Area Health and Safety Skill Area Self-Care Skill Area Motor Skill Area	
ABAS Parent 5-21 year old		
Conceptual Reasoning Domain Social Interactions Domain Practical Functioning Domain Adaptive Behavior Domain Score	Communication Skill Area Functional Academics Skill Area Self-Direction Skill Area Leisure Skill Area Social Skill Area Community Use Skill Area Home Living Skill Area Health and Safety Skill Area Self-Care Skill Area	

ABAS Adult 16-89 year old		
Conceptual Reasoning Domain Social Interactions Domain Practical Functioning Domain Adaptive Behavior Domain Score	Communication Skill Area Functional Academics Skill Area Self-Direction Skill Area Leisure Skill Area Social Skill Area Community Use Skill Area Home Living Skill Area Health and Safety Skill Area Self-Care Skill Area	
Detection Identification Attention Domain Composite	Pediatrics 4-5 year old	
Detection Identification One Back (speed) One Back (accuracy) Attention Domain Composite	Pediatric 6-9 year old	
Detection Identification One Back (speed) One Back (accuracy) Attention Domain Composite	Adult 10-21 year old	

[1] Higher scores indicate better performance (multiplicand = +1).

[2] Lower scores indicate better performance (multiplicand = -1).

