## 10.6. Derived Variables

### 10.6.1. Standardized Scores: Comparison of Individual Scores to Age-Matched Normative Data for [REDACTED] Computerized Cognitive Tests (Age-Adjusted Z-Scores)

A comparison of individual scores to age-matched normative data will also be conducted. The process will be as follows:

- Performance on each neurocognitive outcome measure will be standardized relative to age-matched normative data (i.e., the score will be converted to a z-score by subtracting the age matched mean from the normative sample and dividing by the age-matched standard deviation (SD) from the same normative sample)
- The multiplicand equals 1 for outcome measures for which a higher score is indicative of better cognitive performance and -1 for outcome measures where a lower score is indicative of better cognitive performance. Please see Table 2 for details regarding the multiplicand for each outcome measure.
- The z-score will be calculated as follows:

$$z - Score (z_{ijt}) = \frac{(x_{ijt} - \bar{x}_t)}{SD_t} * Multiplicand$$

Where:

$t$  = is the outcome measure indicator

$i$  = indexes subject  $i$

$j$  = indexes the  $j$ th assessment for subject  $i$

$x$  = cognitive score

$\bar{x}_t$  = mean performance score of the age-matched normative sample for outcome measure  $t$

$SD_t$  = Standard Deviation of the age-matched normative sample for outcome measure  $t$

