**Table 3. Detection**

Age (Years)	Mean	SD
4	2.82934	0.12057
5	2.77951	0.11345
6	2.74635	0.09264
7	2.66173	0.09901
8	2.63129	0.13746
9	2.58581	0.13506
10	2.56241	0.08007
11	2.53830	0.07896
12	2.52938	0.07682
13	2.51597	0.07535

14	2.51298	0.08101
15	2.50910	0.07674
16	2.50538	0.07644
17	2.50197	0.07528
18-34	2.45444	0.07337

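### Whole-year norms put a saw-tooth into the computerised-test z-scores, with a false change of about -0.4 to -0.6 across the 7th birthday, and the SAP does not say which age selects the norm

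*SAP*

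**What the plan says.** SAP 10.6.1: "Performance on each neurocognitive outcome measure will be standardized relative to age-matched normative data". The z-score is formed by "subtracting the age matched mean from the normative sample", dividing by the SD of the same sample and multiplying by +1 or -1 so that higher is better. The norms in Tables 3 to 6 are one row per year of age, starting at 4 (Detection, Identification) or 6 (One Back). Consecutive rows of Table 3 read "6 2.74635 0.09264" and "7 2.66173 0.09901" (age, mean, SD). No interpolation or age-in-months rule is given.

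SAP 8.2 defines one age per visit: age at completion of the Structured Developmental History "will be used as the Visit Age for each visit". Section 10.6.1 does not say whether this age picks the norm row.

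Protocol Table 2-2, footnote 25: "The neurocognitive assessments can for all visits be made within" one month either side of the visit, with a different window for Visit 1 and end of trial. Protocol 8.3.3 has the developmental history collected in connection with the assessments and does not require the same day.

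SAP 10.1 makes z and change in z the endpoints, and 12.2 tabulates change from the prior and from the Initial Assessment. The Attention composite (10.5) averages the speed z-scores, and the haemophilia-adjusted z (10.6.3) takes the age-adjusted z as its input. The Bayley, Wechsler, BRIEF, BASC and ABAS scores are converted through Table 7 and do not use Tables 3 to 6.

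**The concern.** Response speed improves through childhood, but the reference value is flat for twelve months and then jumps. A child who develops exactly as the norms predict gains z between birthdays and loses it at the birthday. SAP 8.2 has the battery given every 6 months, so about every second change from prior crosses a birthday. In a single-arm trial no control group shows the same pattern to set against it. A spurious decline would sit in the tables, listings and individual plots meant to reveal a neurocognitive effect, and the three speed tests step together at age 7.

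A second, separate question is which date fixes the age. If it is the form and not the test, a child near a birthday can be scored on the wrong row.

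**Working it through.** The SAP states no figure for this effect, so there is none to reproduce. Inputs are the age rows of SAP Tables 3 to 6 and the multiplicands in Table 2 (-1 for Detection, Identification and One Back speed; +1 for One Back accuracy).

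**Step for an unchanged raw score.** For a child at the age-6 mean, rescored at age 7 on a speed test:

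step = -(mean6 - mean7) / SD7

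- Detection: -(2.74635 - 2.66173)/0.09901 = -0.85
- Identification: -(2.94156 - 2.87557)/0.07695 = -0.86
- One Back speed: -(3.17567 - 3.07410)/0.11496 = -0.88
- Attention composite, the average of the three unrounded values: -0.87

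The step depends on the child's level because the SDs differ. For One Back speed it runs from -0.45 at 1 SD below the age-6 mean to -1.32 at 1 SD above.

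**Normally developing median child, tested 3 months either side of a birthday.** Assumption: each norm mean holds at mid-year and the path is linear in between. The child is then a quarter of the one-year difference D beyond the younger mean at the first test, and a quarter short of the older mean at the second:

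change = -(D/4) x (1/SD_younger + 1/SD_older)

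| Test | D, 6 to 7 | z at 6.75 | z at 7.25 | change |
|---|---|---|---|---|
| Detection | 0.08462 | +0.23 | -0.21 | -0.44 |
| Identification | 0.06599 | +0.24 | -0.21 | -0.46 |
| One Back speed | 0.10157 | +0.39 | -0.22 | -0.61 |

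With other 6-month pairs spanning the 7th birthday the range is -0.43 to -0.46, -0.43 to -0.48 and -0.46 to -0.77 respectively.

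**Other birthdays, same formula.**

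- Detection: -0.21 (4 to 5), -0.16 (5 to 6), -0.13 (7 to 8), -0.17 (8 to 9).
- Identification: -0.41 (4 to 5), -0.02 (5 to 6), -0.16 (7 to 8), -0.22 (8 to 9).
- One Back speed: -0.16 (7 to 8), -0.14 (8 to 9).
- One Back accuracy: near zero at 6 to 7 (+0.01) and 7 to 8 (-0.06), but -0.34 at 8 to 9.
- At 9 to 10 the formula gives -0.12, -0.25 and -0.22 for the three speed tests, but those rows belong to different platforms (pediatric and adult), so the linear path is doubtful there.

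**Within a year.** From 7.1 to 7.6 years the same child shows a false gain of +0.37, +0.38 and +0.39 on the three speed tests.

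**Effect of the age definition.** Replacing the form date by the test date leaves the 6-to-7 step at -0.85 to -0.88, because the step comes from the whole-year rows. The date matters only when a birthday falls between form and test. With birthdays spread evenly, that share is gap/365: 0% if same day, 14/365 = 4%, 60/365 = 16%. The gaps are assumptions; 60 days needs form and test at opposite ends of the window. Form before and test after the birthday uses the younger row and usually inflates z; the reverse usually deflates it.

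**The case against.** The strongest case on the other side is that this is small and already guarded. The analysis is descriptive. Gains within the year offset the drop. At most birthdays the artefact for a developing median child is a quarter of an SD or less. An expert panel reviews each case with the developmental history. Form and tests share a 6-month schedule and are entered on the same tablets at site (Protocol 12.4), so same-day completion is the natural reading and the date problem may never arise. All of this stands and limits the point. It does not remove a predictable error of about half an SD at one birthday from an endpoint defined as change in z.

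Three stronger readings are tempting, and the documents support none of them.

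- A reader might infer that using the developmental-history age causes the drop of nearly 0.9 SD. It does not; age at test gives the same step. That this age selects the norm row is itself an inference.
- A reader might infer that the step produces false findings under SAP 10.3. That rule compares a patient's level, not the change, with the eTHINK mean and SD, and those values are not given. On the SAP's own norms a developing median child is lowest on the 7th birthday, at half of D over SD7: -0.43, -0.43 and -0.44, under half of 1 SD. A 6-year-old at -0.16, -0.16 and -0.21 with wholly unchanged raw scores would reach -1 on all three speed tests at 7, but that child has made no developmental gain.
- A reader might infer that every birthday lowers every score. Identification at 5 to 6 rises by 0.62 for a child 1 SD above the mean.

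**Conclusion.** The point holds for the computerised battery only. Whole-year norms create a saw-tooth that enters change from prior, change from initial assessment, the Attention composite and the haemophilia-adjusted z. For a normally developing median child it is about -0.44 (Detection), -0.46 (Identification) and -0.61 (One Back speed) across the 7th birthday and about 0.1 to 0.25 SD at most others. Exceptions are Identification at 4 to 5 (-0.41) and One Back accuracy at 8 to 9 (-0.34) on the high side, and Identification at 5 to 6 and One Back accuracy at 6 to 8 near zero. These figures rest on the mid-year, linear assumption; the 0.85 to 0.88 steps need only the tables and an unchanged median raw score.

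Whether the artefact triggers the 1 SD rule cannot be determined. The eTHINK values are absent, and SAP 10.3 pools all ages while 10.6.3 promises tables similar to Tables 3 to 6.

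The lookup age is a separate and smaller ambiguity. It has no effect if form and test share a day, touches at most about 16% of assessments at an assumed 60-day gap, and can act in either direction. The point is worth correcting, but it does not undermine the neurocognitive analysis as a whole.

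**What to change.** 1. State in SAP 8.2 and 10.6.1 that age on the date of each computerised test selects the norm.
2. Report z and change in z from norms (mean and SD) interpolated by exact age, alongside the whole-year z. Interpolate within platform only. Hold the first row below the first mid-year age: the age-4 row before 4.5 for Detection and Identification, the age-6 row before 6.5 for One Back, and the age-10 row from 10.0 to 10.5 on the adult platform. Hold the age-9 row from 9.5 to the 10th birthday. Any step left at age 10 cannot be separated from the platform change and should be labelled so.
3. Flag in the listings every change score that crosses a birthday.

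The cost is a few lines of code and a second set of z-scores that departs from the whole-year lookup. No new data are needed if test dates are captured with the iPad uploads described in SAP 11, which is an assumption. SAP 6 allows revision before database lock.
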